12.4 Interim Analyses and Stopping Rules

Specificity will be assessed once 40 HPV+ patients are evaluable for the primary endpoint, i.e. have both 'HPV-detect' and ¹⁸F-FDG PET-CT results at 3 months following completion of primary RT/CRT. If at this point specificity is <60% it is unlikely that the true specificity at the end of the study will be >85% and therefore consideration will be given to stopping the study due to futility.

The sample size was therefore calculated as follows: Using an A'Hern single stage design with p0 = 0.6 and p1 = 0.85, alpha = 0.05 and power=90%, 27 ¹⁸F-FDG PET-CT negative patients are needed. If 21 or more of

the 27 are also HPV-detect negative, it will be assumed that the true specificity is greater than 60% and the study will continue. Assuming a prevalence of 25% of residual disease of on 18F-FDG PET-CT, 40 HPV+ patients are needed at interim analysis.

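### The interim futility threshold is given as two different values (observed specificity below 60%, and 21 of 27), and the trigger of 40 patients does not follow from 27 PET-negatives at 25% prevalence

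*Protocol*

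**What the plan says.** All the relevant text is in Protocol section 12.4, Interim Analyses and Stopping Rules.

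- Timing: "Specificity will be assessed once 40 HPV+ patients are evaluable for the primary endpoint", that is, once they have both the assay result and the PET-CT result at 3 months.
- First statement of the threshold: "If at this point specificity is <60% it is unlikely that the true specificity at the end of the study will be >85" per cent. The consequence is that "consideration will be given to stopping the study due to futility".
- Design: "Using an A'Hern single stage design with p0 = 0.6 and p1 = 0.85, alpha = 0.05 and power=90" per cent, from which "27 ¹⁸F-FDG PET-CT negative patients are needed".
- Second statement of the threshold, which applies to a count of at least 21: "the 27 are also HPV-detect negative, it will be assumed that the true specificity is greater than 60% and the study will continue".
- Trigger: "Assuming a prevalence of 25% of residual disease of on 18F-FDG PET-CT, 40 HPV+ patients are needed at interim analysis".

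Two other places supply context. Section 12.2.1 defines specificity among PET-negative patients only, so the denominator at the interim is the PET-negative count and not 40. Section 12.1 plans on a true specificity of 95% and uses the same 25% prevalence of residual disease.

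**The concern.** The figure of 60% is used for two different quantities. In the first paragraph it is compared with the specificity assessed at the look, and the same sentence contrasts that value with the true specificity. Read plainly, it is a cut-off on the observed proportion. In the second paragraph 60% is p0, the null value of the true specificity, and the observed cut-off is 21/27, or 77.8%. These are different thresholds, and section 12.4 does not say which one governs.

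The trigger raises a second problem. The text derives 40 patients from the prevalence alone, but the division does not give 40. At 40 evaluable patients the expected PET-negative count is 30, and the only cut-off supplied is for 27.

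This is the only stopping rule in the protocol. A committee that receives, say, 19 of 27 cannot tell from section 12.4 whether the futility criterion has been met.

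**Working it through.** **Inputs, all from Protocol section 12.4:** p0 = 0.60, p1 = 0.85, alpha = 0.05 (one-sided, as in the A'Hern design), power 90%, n = 27 PET-negatives, boundary 21, prevalence of residual disease 25%, trigger 40 evaluable. The planned true specificity of 0.95 is from section 12.1.

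**1. The A'Hern design reproduces.** With X ~ Binomial(27, p):

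- alpha = P(X ≥ 21 | p = 0.60) = 0.0421
- power = P(X ≥ 21 | p = 0.85) = 0.9014

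A search over n from 15 to 44 shows that 27 is the smallest n with alpha ≤ 0.05 and power ≥ 0.90. The figures 27 and 21 are correct.

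**2. The two thresholds on the same 27 patients.**

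- Observed below 60%: 16/27 = 59.3% and 17/27 = 63.0%, so the criterion is met at X ≤ 16.
- A'Hern boundary missed: 20/27 = 74.1% and 21/27 = 77.8%, so it is missed at X ≤ 20.
- The statements agree at X ≤ 16 and at X ≥ 21. They part at X = 17 to 20.

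The last column is the third minus the second.

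| True specificity | P(X ≤ 16) | P(X ≤ 20) | P(17 ≤ X ≤ 20) |
|---|---|---|---|
| 0.60 | 0.542 | 0.958 | 0.416 |
| 0.70 | 0.157 | 0.744 | 0.587 |
| 0.75 | 0.053 | 0.529 | 0.476 |
| 0.80 | 0.011 | 0.287 | 0.276 |
| 0.85 | 0.001 | 0.099 | 0.097 |
| 0.95 | <0.0001 | 0.0003 | 0.0003 |

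Under the observed-60% reading, an assay whose true specificity is exactly 60% escapes the futility criterion with probability 1 − 0.542 = 0.458. Under the A'Hern boundary that probability is 0.042. The stated error rates therefore describe only the second statement.

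**3. The trigger.**

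- PET-negative share = 1 − 0.25 = 0.75.
- Patients needed for 27 expected PET-negatives = 27/0.75 = 36, against 40 stated.
- Expected PET-negatives at 40 = 40 × 0.75 = 30.
- Prevalence at which 27 would come from exactly 40 = 1 − 27/40 = 32.5%, not 25%.

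Two undeclared routes lead to about 40. A 10% loss allowance gives 36/0.90 = 40, but the 40 are defined as already evaluable, so no loss remains to allow for. An assurance margin fits better: with N evaluable and PET-negatives ~ Binomial(N, 0.75), P(at least 27) is 0.897 at N = 40 and 0.588 at N = 36.

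**4. Cut-offs for other denominators, same p0, p1 and alpha.**

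| PET-negatives | Smallest cut-off with alpha ≤ 0.05 | Exact alpha | Exact power |
|---|---|---|---|
| 27 | 21 | 0.042 | 0.901 |
| 30 | 23 | 0.044 | 0.930 |
| 33 | 25 | 0.044 | 0.951 |

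**The case against.** The strongest defence is that there is one rule. The second paragraph presents itself as the calculation behind the first and uses p0 = 0.6, so the 60% in the first paragraph may be loose shorthand for the null value, with 21/27 as its working form. That is probably the intention, and it is why the repair is small. It does not rescue the wording, which applies 60% to the result at the look.

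A reader might infer that section 12.4 gives opposite orders, to continue and to stop, for 17 to 20 of 27. The text does not go that far. It says the study continues at 21 or more, not only at 21 or more, and it does not say to continue whenever the observed value is 60% or above. That range is left unresolved.

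A reader might also infer that the stated alpha and power fail because 40 patients will usually yield a count other than 27. They hold if the first 27 PET-negatives are assessed. Applying 21 to 30 patients would raise alpha to 0.176, but the protocol ties 21 to 27 and nowhere proposes that use. Handling of other denominators may also be set out in the SAP, which was not available here.

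Three further points stand. At the planned specificity of 0.95 the disputed range is almost never reached. Forty is on the safe side of 36. The look is non-binding, is for futility only, goes to an independent committee that includes a statistician (section 13.2), and does not affect patient management because clinicians do not see the assay results (section 4).

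**Conclusion.** Section 12.4 is wrong as written on two counts.

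- **Threshold.** It is stated as 16/27 or fewer and, through the A'Hern design, as failure to reach 21/27. Results of 17 to 20 are unresolved. This matters little if the assay performs as planned (0.03% at 0.95) and a good deal if it does not (10% at 0.85, 28% at 0.80, 59% at 0.70), which is when a futility rule is needed.
- **Trigger.** Forty does not follow from 27 PET-negatives at 25% prevalence; 36 does. This is the milder part. Forty is defensible as a margin giving about 90% assurance of 27 PET-negatives, but the protocol gives no such reason.

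The probabilities assume independent patients, exact binomial counts and, for the trigger, a true prevalence of 25%. The threshold conflict itself rests on reading the first statement as an observed value, which is its natural sense. The A'Hern figures are sound, and nothing here implies a larger type I error for the primary analysis. Severity is moderate: a correction of wording to make before the interim look.

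**What to change.** 1. Keep one rule, the A'Hern boundary. Reword the 60% sentence so that 60% is the null value p0, and say that stopping will be considered when the boundary is missed.
2. Settle the trigger in one of two ways:
   - hold the look when 27 evaluable PET-negative HPV+ patients are available, expected at about 36 evaluable patients; or
   - keep 40 evaluable patients, state that this is a margin giving about 90% assurance of at least 27 PET-negatives, and say whether the rule applies to the first 27 or uses the exact cut-off for the count observed (for example 21/27, 23/30 or 25/33). The second option also needs a line on what happens if fewer than 27 are available.
3. Do not simply replace 40 with 36 evaluable patients. That would reach 27 PET-negatives only 59% of the time.

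The cost is a protocol wording change, with no additional patients or samples.

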13. STUDY MANAGEMENT

13.1 Project Management Group (PMG)

A Project Management Group (PMG) will be set up and will include the Chief Investigator, ICR-CTSU Scientific Lead, Co-investigators and identified collaborators, the Study Statistician and Project Manager. Where possible, membership will include a lay/consumer representative. The PMG will meet at regular intervals, and at least annually. Notwithstanding the legal obligations of the Sponsor and Chief Investigator, the PMG have operational responsibility for the conduct of the study. The Committee's terms of reference, roles and responsibilities will be defined in a charter issued by ICR-CTSU.

13.2 Independent Data Monitoring and Steering Committee (IDMSC)

A joint Independent Data Monitoring and Steering Committee (IDMSC) will be set up to, monitor the data produced by the study, put these data into overall context and supervise the progress of the study towards its interim and overall objectives. The IDMSC will comprise an independent Chairman and at least two further independent members with clinical or statistical expertise (at least one member must be a statistician).

The IDMSC will meet in confidence at regular intervals, and at least annually. A summary of findings and any recommendations will be produced following each meeting. This summary will be submitted to the PMG and if required, the main REC.

The Committee's terms of reference, roles and responsibilities will be defined in a charter issued by ICR-CTSU.

14. RESEARCH GOVERNANCE

14.1 Sponsor Responsibilities

The Sponsor of this study is the Institute of Cancer Research (ICR).

14.2 Participating Site Responsibilities

Responsibilities of participating sites are defined in an agreement between the individual participating site and the Sponsor.

15. STUDY ADMINISTRATION & LOGISTICS

15.1 Site activation

Before activating the study, participating sites are required to sign an agreement accepting responsibility for all study activity which takes place within their site.

Sites may commence recruitment once the site agreement has been signed by all required signatories, the required study documentation is in place (as specified by ICR-CTSU), a site initiation (teleconference) has taken place and ICR-CTSU has confirmed in writing that the site is officially open to recruitment.

15.2 Data Acquisition

Electronic (e) Case Report Forms (CRF) will be used for the collection of study data. ICR-CTSU will provide guidance to sites to aid the completion of the eCRFs. The Project Management Group reserves the right to amend or add to the eCRF template as appropriate. Such changes do not constitute a protocol amendment, and revised or additional forms should be used by sites in accordance with the guidelines provided by ICR-CTSU.

The clinical data should be reported on the INOVATE eCRFs to the ICR-CTSU in a timely manner. Specific guidance on how data will be collected will be detailed in study guidance notes. On receipt at ICR-CTSU, eCRFs will be recorded as received and any missing data will be reported to the originating site.

15.3 Central Data Monitoring

Once data has been entered on the eCRF by the site personnel, ICR-CTSU will review it for compliance with the protocol, and for inconsistent or missing data. Should any missing data or data anomalies be found, queries will be raised for resolution by the site.

15.4 Completion of the Study and Definition of Study End Date

The study end date is deemed to be the date of last data capture.

15.5 Archiving

Essential study documents should be retained according to local policy and for a sufficient period for possible inspection by the regulatory authorities (at least 5 years after the date of last data capture). Documents should be securely stored and access restricted to authorised personnel.

16. PATIENT PROTECTION AND ETHICAL CONSIDERATIONS

16.1 Study Approvals

INOVATE has been approved by the Sponsor's Committee for Clinical Research (CCR).

ICR-CTSU, on behalf of the Sponsor, will ensure that the study has received ethics approval from a research ethics committee and Health Research Authority (HRA) approval. Before entering patients, the Principal Investigator at each site is responsible for submitting this protocol and Site Specific Information to gain either confirmation of capacity and capability (for participating sites in England) or local Research and Development approval (for participating sites in Scotland, Wales or Northern Ireland).

16.2 Study Conduct

This study will be conducted according to the approved protocol and its amendments, supplementary guidance supplied by the Sponsor and in accordance with the UK Policy Framework for Health & Social Care and the principles of GCP.

16.3 Patient Confidentiality

Patients will be asked to consent to their initials being collected at study entry in addition to their date of birth, hospital number, postcode and NHS number or equivalent to allow linkage with routinely collected NHS data.

Biological samples will be labelled with date of birth and study ID to ensure accuracy in handling the samples.

Each investigator should keep a separate log of all participants' Study IDs, names, addresses and hospital numbers. The investigator must retain study documents (e.g. participants' written consent forms) in strict confidence. The investigator must ensure the participants' confidentiality is maintained at all times.

Representatives of ICR-CTSU may require access to participants' hospital notes for quality assurance purposes. ICR-CTSU will maintain the confidentiality of participants at all times and will not reproduce or disclose any information by which participants could be identified.

16.4 Data Protection

All parties must comply with all applicable data protection laws.

16.5 Liability

Indemnity to meet the potential legal liability of investigators participating in this study is provided by the usual NHS indemnity arrangements.

17. FINANCIAL MATTERS

This study is investigator designed and led and has been approved by the Medical Research Council Developmental Pathway Funding Scheme.

ICR has received funding from the Medical Research Council for the central coordination of the study. In the UK, the study meets the criteria for R&D support as outlined in the Statement of Partnership on Non-Commercial R&D in the NHS in England. The study is part of the National Institute for Health Research Clinical Research Network (NCRN) portfolio by virtue of its approval by the MRC. NCRN resources should therefore be made available for the study to cover UK specific research costs.

18. TISSUE SHARING POLICY

The custodian of the samples will be the Project Management Group. Proposals for future research projects involving the material will be considered by the PMG.

19. PUBLICATION POLICY

The main study results will be published in a peer-reviewed journal, on behalf of all collaborators. The manuscript will be prepared by a writing group, consisting of members of the PMG. Participating clinicians may be selected to join the writing group on the basis of intellectual and time input. All participating clinicians will be acknowledged in the publication.

Any presentations and publications relating to the study must be authorised by the PMG. Authorship of any secondary publications e.g. those relating to sub-studies, will reflect intellectual and time input into these studies.

No investigator may present or attempt to publish data relating to the INOVATE study without prior permission from the PMG.

20. ASSOCIATED STUDIES – STAKEHOLDER ANALYSIS AND HEALTH ECONOMICS STUDY

The National Institute for Health Research London in vitro Diagnostics Cooperative (NIHR London IVD) at Imperial will undertake stakeholder analyses to understand risks, adoption barriers and assess potential impact of HPV-detect in the NHS. Actual end-users' and potential key stakeholders will be interviewed to identify and understand perceived barriers to adoption, needs for improvement adaptation of HPV-detect and potential impact for the NHS.

Workflow and clinical pathway mapping analysis will be undertaken in order to understand the impact of implementing HPV-detect on hospital resources. Health economic modeling for cost effectiveness analysis will be carried out by generating costs for clinical pathways with, and without HPV-detect. The cost benefits will be captured in a decision analytic model with consequences for the patients (changes in short and long term QOL) and cost savings to the NHS. The impact of test sensitivity and specificity on cost will be modelled using sensitivity analyses.

The pathway mapping and health economic analyses will be carried out in parellell with the clinical study in order to model the future impact of HPV-detect implementation. These analyses will be carried out over a period of **9 months**. The stakeholder analyses will require 6 months and will be conducted during the study. The health economic analyses will require 3 months and will be performed once the final results of the study become available prior to study publication.

Further details of the stakeholder analysis and health ecomonics sub-study will be added to the protocol by substantial amendment. Sites will be notified by ICR-CTSU when the sub-study will commence.

